4.3 Serious Adverse Events

Classification of Serious Adverse Events is defined as follows:

Death of Subject

An event that results in the death of a subject.

Life-Threatening

An event that, in the opinion of the investigator, would have resulted in immediate fatality if medical intervention had not been taken. This does not include an event that would have been fatal if it had occurred in a more severe form.

| | |
|--|--|
| Hospitalization or Prolongation of Hospitalization | An event that results in an admission to the hospital for any length of time or prolongs the subject's hospital stay. This does not include an emergency room visit or admission to an outpatient facility. |
| Congenital Anomaly | An anomaly detected at or after birth, or any anomaly that results in fetal loss. |
| Persistent or Significant Disability/Incapacity | An event that results in a condition that substantially interferes with the activities of daily living of a study subject. Disability is not intended to include experiences of relatively minor medical significance such as headache, nausea, vomiting, diarrhea, influenza, and accidental trauma (e.g., sprained ankle). |
| Important Medical Event Requiring Medical or Surgical Intervention to Prevent Serious Outcome | An important medical event that may not be immediately life-threatening or result in death or hospitalization, but based on medical judgment may jeopardize the subject and may require medical or surgical intervention to prevent any of the outcomes listed above (i.e., death of subject, life-threatening, hospitalization, prolongation of hospitalization, congenital anomaly, or persistent or significant disability/incapacity). Additionally, any elective or spontaneous abortion or stillbirth is considered an important medical event. Examples of such events include allergic bronchospasm requiring intensive treatment in an emergency room or at home, blood dyscrasias or convulsions that do not result in inpatient hospitalization, or the development of drug dependency or drug abuse. |

4.4 Adverse Event Definition of Severity Grade

When criteria are available, events should be graded to the 5 criteria as described in the National Cancer Institute Common Terminology Criteria for Adverse Events (CTCAE) Version 5.0,¹ which can be accessed at: https://ctep.cancer.gov/protocoldevelopment/electronic_applications/docs/CTCAE_v5_Quick_Reference_8.5x11.pdf.

If no grading criteria are provided for the reported event, the event should be graded as mild, moderate, or severe per the Investigator's judgment.

| | |
|-----------------|---|
| Mild | Asymptomatic or mild symptoms; clinical or diagnostic observations only; intervention not indicated. |
| Moderate | Minimal, local or noninvasive intervention indicated; limiting age-appropriate instrumental activities of daily living (ADL). |
| Severe | Severe or medically significant but not immediately life threatening; hospitalization or prolongation of hospitalization indicated; disabling; limiting self-care ADL. Life-threatening consequences; urgent intervention indicated. Death related to AE. |

4.5 Definition of Relationship to Study Drug

Relationship to study drug is defined as follows:

| | |
|----------------------------------|---|
| Reasonable Possibility | After consideration of factors including timing of the event, biologic plausibility, clinical judgment, and potential alternative causes, there is sufficient evidence (information) to suggest a causal relationship. |
| No Reasonable Possibility | After consideration of factors including timing of the event, biologic plausibility, clinical judgment, and potential alternative causes, there is insufficient evidence (information) to suggest a causal relationship |

4.6 Recording Data and Analyses of Safety Findings

Adverse events will be coded using the Medical Dictionary for Regulatory Activities (MedDRA). The number and percentage of subjects with treatment-emergent AEs (i.e., any event that begins or worsens in severity after initiation of study drug through 140 days post-study drug dosing) will be tabulated by primary MedDRA System Organ Class (SOC) and preferred term (PT). The tabulation of the number of subjects with treatment-emergent AEs by severity grade and relationship to study drug also will be provided. Subjects reporting more than one AE for a given MedDRA preferred term will be counted only once for that term using the most severe grade for the severity grade table and the most related for the relationship to study drug tables. Subjects reporting more than one type of event within a SOC will be counted only once for that SOC.

4.7 Reporting Adverse Events and Intercurrent Illnesses

In the event of an SAE, whether associated with study drug or not, the Investigator will notify Clinical Pharmacovigilance within 24 hours of the site being made aware of the SAE by entering the SAE data into the electronic data capture (EDC) system. SAEs that occur prior to the site having access to the RAVE® system, or if RAVE is not operable, should be documented on the SAE non-CRF forms and emailed (preferred route) or faxed to Clinical Pharmacovigilance within 24 hours of the site being made aware of the SAE.

Email: [contact]

FAX to: [contact]

For safety concerns, contact the Immunology Safety Team at:

Immunology Safety Team Dept.

R48S, Bldg. AP31-2

[name]

Office: [contact]

Email: [contact]

For any subject safety concerns, please contact the physician listed below:

AbbVie

[name],

[name]

Contact Information:

Office/Mobile:

Email:

In emergency situations involving study subjects when the primary Therapeutic Area Medical Director is not available by phone, please contact the 24-hour AbbVie Medical Escalation Hotline where your call will be re-directed to a designated backup AbbVie Therapeutic Area Medical Director:

[contact]

COVID-19 Pandemic-Related Acceptable Protocol Modifications

Supplemental study case report forms should be completed in the event of COVID-19 related missed/virtual visits, study drug interruptions or discontinuations, or adverse events (including capture of specific signs/symptoms of infection and testing results).

COVID-19 infections should be captured as adverse events. If the event meets the criteria for a serious adverse event (SAE), then follow the SAE reporting directions per the protocol and above. The following COVID-19 related supplemental eCRFs should be completed:

- COVID -19 Supplemental Signs/ Symptoms
- COVID-19 Status Form

If a subject has a confirmed or suspected COVID-19 infection and study drug was interrupted, the investigator should contact the sponsor emergency medical contact listed above before reintroducing study drug.

4.8 Reporting Product Complaints

Product Complaints occurring during the study will be followed-up to a satisfactory conclusion. All follow-up information is to be reported to the Sponsor (or an authorized representative) and documented in source as required by the Sponsor. Product Complaints associated with adverse events will be reported in the study summary. All other complaints will be monitored on an ongoing basis.

Product Complaints may require return of the product with the alleged complaint condition. In instances where a return is requested, every effort should be made by the investigator to return the product within 30 days. If returns cannot be accommodated within 30 days, the site will need to provide justification and an estimated date of return.

5 COUNTRY-SPECIFIC REQUIREMENTS

5.1 SUSAR Reporting

AbbVie will be responsible for Suspected Unexpected Serious Adverse Reaction (SUSAR) reporting for the Investigational Medical Product (IMP) in accordance with global and local guidelines, and Appendix A of the Investigator's Brochure will serve as the Reference Safety Information (RSI). The RSI in effect at the start of a Development Safety Update Report (DSUR) reporting period serves as the RSI during the reporting period. For follow-up reports, the RSI in place at the time of occurrence of the 'suspected' Serious Adverse Reaction will be used to assess expectedness.

5.2 Additional Eligibility Criteria

For subjects in some countries, such as China, Korea, Malaysia, Singapore, Hong Kong, Taiwan, and Japan, inadequate response to MTX is defined as lack of efficacy after minimum 12 weeks duration of therapy at MTX dose ≥ 7.5 mg/week or as required per local authorities.

5.3 Additional Requirements-France

Collection of race and ethnicity information is not required.

5.4 Additional Laboratory Requirements

If required by country regulatory authorities, subjects who initiate or increase dose of MTX during the study should undergo ALT, AST, creatinine and complete blood count (CBC) testing every 4 weeks for a 12 week period.

6 STUDY DRUG

6.1 Treatments Administered

The study drug (risankizumab or placebo) will be administered by a healthcare professional in the form of 2 subcutaneous injections of 75 mg per injection at the visits listed in Section 2.1. For additional details on dispensing study drug in the event of home administration due to the COVID-19 pandemic, see Section 3.11.

Risankizumab will be provided by AbbVie as solution for injection in pre-filled syringes (PFS).

Risankizumab will be administered as an initial dose, a second dose 4 weeks later, and q12w thereafter.

Study drug administration instructions will be provided separately.

6.2 Packaging and Labeling

Study drug packaged in 75 mg PFS will be provided in both open-label and blinded fashion and packaged in cartons containing 1 syringe per carton. Each kit will be labeled as required per local requirements. Each kit label will contain a unique kit number. This kit number is assigned to a subject via Interactive Response Technology (IRT) and encodes the appropriate study drug to be administered at the subjects corresponding study visit.

All labels must remain affixed to the study drug at all times and should never be removed for any reason. All blank spaces should be completed by site staff prior to dispensing to subject.

Storage and Disposition of Study Drug

Risankizumab or placebo PFS must be kept protected from light in the original packaging, in a refrigerator between 2° to 8°C (36° to 46°F). Study drug must not be frozen at any time. The investigational products are for investigational use only and are to be used only within the context of this study. The study drug supplied for this study must be maintained under adequate security and stored under the conditions specified on the label until dispensed for subject use or destroyed on site as appropriate. A temperature log must be maintained for documentation.

The refrigerator temperature must be recorded each business day. Malfunctions or temperature excursions must be reported to the Sponsor immediately upon notice. Study drug should be quarantined and not dispensed until AbbVie or AbbVie Temperature Excursion Management System (ATEMS) deems the drug as acceptable.

6.3 Method of Assigning Subjects to Treatment Groups

This is a Phase 3, global, multi-center study that will evaluate subjects with moderately to severely active psoriatic arthritis. Period 1 is a 24-week randomized, double-blind, placebo-controlled, parallel-group period. Eligible subjects will be randomized to risankizumab or placebo in a 1:1 ratio for Period 1. After the Week 24 assessments are performed, Period 2 begins. During Period 2, all subjects will receive risankizumab. To maintain the blind to the original treatment allocation, treatment at the Week 24 Visit will be blinded: subjects who were randomized to placebo will receive blinded risankizumab, and those randomized to risankizumab will receive 1 dose of blinded placebo. At Week 28 and for the remaining dosing visits all subjects will receive open-label risankizumab 150 mg q12w.

At the Screening Visit, all subjects will be assigned a unique subject number through the use of the IRT. Randomization will be stratified by current use of csDMARD (0 vs ≥ 1), number of prior biologic therapies (0 vs ≥ 1), and extent of psoriasis ($\geq 3\%$ BSA or $< 3\%$ BSA) at Baseline.

For subjects who do not meet the study selection criteria, the site personnel must login to the IRT system and identify the subject as a screen failure.

Subjects who are enrolled will retain their subject number assigned at the Screening Visit throughout the study. Upon receipt of study drug, the site will acknowledge receipt in the IRT system.

Contact information and user guidelines for IRT use will be provided to each site.

6.4 Selection and Timing of Dose for Each Subject

Risankizumab 150 mg or matching placebo dose subcutaneously (SC, 2 \times 75 mg PFS) administered at Week 0, 4, 16, 24, 28, and q12w thereafter is selected for this study.

6.5 Drug Accountability

The investigator or his/her designated and qualified representatives will administer study drug only to subjects enrolled in the study in accordance with the protocol. The study drug must not be used for reasons other than that described in the protocol.

An overall accountability of the study drug will be performed and verified by the AbbVie monitor throughout the treatment period. The monitor will review study drug accountability on an ongoing basis. Final accountability will be verified by the monitor at the end of study drug treatment at the site.

Stand-alone investigational product administration guidelines for sites will be provided by the sponsor.

The study drug start date and the last dose of the regimen will be documented in the subject's source documents and recorded on the appropriate eCRF. The status of each kit and the date of reconciliation will be documented in the IRT system. The monitor will review study drug accountability on an ongoing basis.

Upon completion of or discontinuation from the treatment, all study drug will be returned to AbbVie (or designee) or destroyed on site. All destruction procedures will be according to instructions from the Sponsor and according to local regulations following completion of drug accountability procedures.

7 References:

1. US Dept. of Health and Human Services. Common Terminology Criteria for Adverse Events (CTCAE) Version 5.0. November 27, 2017. Available from: https://ctep.cancer.gov/protocoldevelopment/electronic_applications/docs/CTCAE_v5_Quick_Reference_8.5x11.pdf.
5. Gestel AM van, Haagsma CJ, Riel PLCM van. Validation of rheumatoid arthritis improvement criteria that include simplified joint counts. *Arthritis Rheum.* 1998;41(10):1845-50.

APPENDIX A. STUDY SPECIFIC ABBREVIATIONS AND TERMS

| Abbreviation | Definition |
|---------------|--|
| Ab | Antibody |
| ADA | Anti-drug antibody |
| AE | Adverse event |
| Ag | Antigen |
| ALT | Alanine aminotransferase |
| AST | Aspartate aminotransferase |
| BASDAI | Bath Ankylosing Spondylitis Disease Activity Index |
| BIO-IR | Inadequate response to 1 or 2 biologic therapies or intolerance |
| BP | Blood pressure |
| BSA-PsO | Body surface area-psoriasis |
| BUN | Blood urea nitrogen |
| CASPAR | Classification Criteria for PsA |
| CBC | Complete blood count |
| CCP | Cyclic-citrullinated peptide |
| CKD-EPI | Chronic Kidney Disease Epidemiology Collaboration |
| csDMARD | Conventional synthetic disease modifying anti-rheumatic drug |
| DAS28 | Disease Activity Score 28 |
| ECG | Electrocardiogram |
| eCRF | Electronic case report form |
| EDC | Electronic data capture |
| eGFR | Estimated glomerular filtration rate |
| EQ-5D-5L | EuroQol-5D-5L |
| FACIT-Fatigue | Functional Assessment of Chronic Illness Therapy-Fatigue |
| FSH | Follicle-stimulating hormone |
| GGT | Gamma-glutamyl transferase |
| GRAPPA | Group for Research and Assessment of Psoriasis and Psoriatic Arthritis |
| HAQ-DI | Health Assessment Questionnaire-Disability Index |
| HBc | Hepatitis B core |
| HBs | Hepatitis B surface |
| hCG | Human Chorionic Gonadotropin |

| | |
|--------|---|
| HCV | Hepatitis C virus |
| HDL-C | High-density lipoprotein-cholesterol |
| HIV | Human immunodeficiency virus |
| HRU | Health Resource Utilization |
| hsCRP | High sensitivity C-Reactive Protein |
| IMP | Investigational Medical Product |
| IRT | Interactive Response Technology |
| LDI | Leeds Dactylitis Index |
| LDL-C | Low-density lipoprotein-cholesterol |
| LEI | Leeds Enthesitis Index |
| MedDRA | Medical Dictionary for Regulatory Activities |
| nAb | Neutralizing antibody |
| OOW | Out of window |
| PASI | Psoriasis Area Severity Index |
| PD | Premature Discontinuation |
| PFS | Pre-filled syringe |
| PGA | Physician's Global Assessment |
| PK | Pharmacokinetic(s) |
| PPD | Purified Protein Derivative |
| PRO | Patient-reported outcome |
| PsA | Psoriatic Arthritis |
| PsARC | Psoriatic Arthritis Response Criteria |
| PT | Preferred term |
| PtGA | Patient's Global Assessment |
| RBC | Red blood cell |
| SAE | Serious adverse event |
| SC | Subcutaneous(ly) |
| SF-36 | 36-Item Short Form Health Survey |
| SJC | Swollen joint count |
| SOC | System Organ Class |
| SPARCC | Spondyloarthritis Research Consortium of Canada |
| SUSAR | Suspected Unexpected Serious Adverse Reaction |
| TA MD | Therapeutic Area Medical Director |

| | |
|------|---|
| TB | Tuberculosis |
| TJC | Tender joint count |
| ULN | Upper limit of normal |
| VAS | Visual analogue scale |
| WBC | White blood cell |
| WPAI | Work Productivity and Activity Impairment |

APPENDIX B. CASPAR CRITERIA

Table. The CASPAR classification criteria for PsA

To be classified as having PsA, a patient must have inflammatory articular disease (joint, spine, enthesal) with ≥ 3 of the following 5 points:

| Criterion | Description |
|--|--|
| 1. Evidence of psoriasis (one of a, b, c): (a) Current psoriasis ^a | Psoriatic skin or scalp disease currently present, as judged by a rheumatologist or a dermatologist |
| (b) Personal history of psoriasis | A history of psoriasis obtained from patient or family physician, dermatologist, rheumatologist, or other qualified health care professional |
| (c) Family history of psoriasis | A history of psoriasis in a first- or second-degree relative by patient report |
| 2. Psoriatic nail dystrophy | Typical psoriatic nail dystrophy, including onycholysis, pitting, and hyperkeratosis observed on current physical examination |
| 3. Negative test result for RF | By any method except latex but preferably by ELISA or nephelometry, according to the local laboratory reference range |
| 4. Dactylitis (one of a, b): (a) Current | Swelling of an entire digit |
| (b) History | A history of dactylitis recorded by a rheumatologist |
| 5. Radiological evidence of juxta-articular new bone formation | Ill-defined ossification near joint margins (excluding osteophyte formation) on plain x-ray films of hand or foot |

CASPAR, Classification criteria for Psoriatic ARthritis; PsA, psoriatic arthritis; RF, rheumatoid factor; ELISA, enzyme-linked immunosorbent assay.

^a Current psoriasis scores 2; all other items score 1.

APPENDIX C. CLINICAL CRITERIA FOR DIAGNOSING ANAPHYLAXIS

Anaphylaxis² is highly likely when any one of the following 3 criteria is fulfilled:

1. Acute onset of an illness (minutes to several hours) with involvement of the skin, mucosal tissue, or both (e.g., generalized hives, pruritus or flushing, swollen lips tongue-uvula) AND AT LEAST ONE OF THE FOLLOWING:
 - Respiratory compromise (e.g., dyspnea, wheeze-bronchospasm, stridor, reduced peak expiratory flow, hypoxemia)
 - Reduced BP or associated symptoms or end-organ dysfunction (e.g., hypotonia [collapse], syncope, incontinence)
2. Two or more of the following that occur rapidly after exposure to a likely allergen (study drug) for a subject within minutes to several hours:
 - Involvement of the skin-mucosal tissue (e.g., generalized hives, itch-flush, swollen lips-tongue-uvula)
 - Respiratory compromise (e.g., dyspnea, wheeze-bronchospasm, stridor, reduced PEF, hypoxemia)
 - Reduced BP or associated symptoms (e.g., hypotonia [collapse], syncope, incontinence)
 - Persistent gastrointestinal symptoms (e.g., crampy abdominal pain, vomiting)
3. Reduced BP after exposure to known allergen (study drug) for that subject (within minutes to several hours), with systolic BP of less than 90 mmHg or greater than 30% decrease from that subject's baseline BP (Day 1).

APPENDIX D. JOINT ASSESSMENT

Joint counts will be performed by assessor(s) who must be well trained and part of the site personnel. Whenever possible, the same evaluator should perform these assessments at all visits.

Number of Tender Joints:

The 68 joints assessed for tenderness include the 2 temporomandibular, 2 sternoclavicular, 2 acromioclavicular joints, 2 shoulders, 2 elbows, 2 wrists, 10 metacarpophalangeal, 10 proximal interphalangeal, 8 distal interphalangeal joints of the hands, the 2 hips, 2 knees, 2 ankles 2 mid-tarsal, 10 metatarsophalangeal, and 10 proximal interphalangeal joints of the feet.

Joints are to be scored as either tender (1) or not tender (0), replaced (9) or not assessed (99).

Number of Swollen Joints:

The 66 joints to be examined for swelling are the same as those examined for tenderness, however excluding both hip joints.

Joints are to be scored as either swollen (1) or not swollen (0), replaced (9) or not assessed (99).

Synovial fluid and/or soft tissue swelling but not bony overgrowth represents a positive result for swollen joint count.

APPENDIX E. AMERICAN COLLEGE OF RHEUMATOLOGY 20 RESPONSE (ACR20)

ACR RESPONSE CRITERIA^{3,4}

ACR 20:

- At least 20% improvement in SJC* compared to baseline **AND**
- At least 20% improvement in TJC* compared to baseline **AND**
- At least 20% improvement in at least 3 out of the following 5 variables:
 1. Patient's assessment of pain on VAS
 2. Patient's global assessment of the disease on VAS
 3. Investigator's global assessment of the disease on VAS
 4. Patient's assessment of disability on HAQ
 5. Acute phase reactant (serum CRP)

ACR 50:

- At least 50% improvement in SJC* compared to baseline **AND**
- At least 50% improvement in TJC* compared to baseline **AND**
- At least 50% improvement in at least 3 out of the following 5 variables:
 1. Patient's assessment of pain on VAS
 2. Patient's global assessment of the disease on VAS
 3. Investigator's global assessment of the disease on VAS
 4. Patient's assessment of disability on HAQ
 5. Acute phase reactant (serum CRP)

ACR 70:

- At least 70% improvement in SJC* compared to baseline **AND**
- At least 70% improvement in TJC* compared to baseline **AND**
- At least 70% improvement in at least 3 out of the following 5 variables:
 1. Patient's assessment of pain on VAS

2. Patient's global assessment of the disease on VAS
3. Investigator's global assessment of the disease on VAS
4. Patient's assessment of disability on HAQ
5. Acute phase reactant (serum CRP)

* SJC and TJC are evaluated according to the complete joint count (see [Appendix D](#)).

APPENDIX F. DISEASE ACTIVITY SCORE(DAS)28 – HSCRIP

DAS28-hsCRP⁵ will be calculated taking the following variables into account:

- TJC (on 28 joints)
- SJC (on 28 joints)
- Patient's global assessment of the disease on VAS (0 – 100)
- Serum hsCRP level (mg/L)

APPENDIX G. PASI SCORE DEFINITIONS AND USE

The PASI score is an established measure of clinical efficacy for psoriasis medications.⁶

The PASI is a tool which provides a numeric scoring for patients overall psoriasis disease state, ranging from 0 to 72. It is a linear combination of percent of surface area of skin that is affected and the severity of erythema, induration, and desquamation over four body regions.

The endpoints used are based on the percent reduction from baseline, generally summarized as a dichotomous outcome based on achieving over an X% reduction (or PASIX), where X is 50, 75, 90, and 100.

To calculate the PASI score, the four main body areas are assessed: **head (h), trunk (t), upper extremities (u) and lower extremities (l)**. These correspond to 10, 30, 20 and 40% of the total body area respectively.

The **area of psoriatic involvement** of these four areas (Ah, At, Au, and Al) is given a numerical value: 0 = no involvement, 1 = < 10%, 2 = 10 to < 30%, 3 = 30 to < 50%, 4 = 50 to < 70%, 5 = 70 to < 90%, and 6 = 90 to 100% involvement.

The **signs of severity, erythema (E), induration (I) and desquamation (D)** of lesions are assessed using a numeric scale 0 – 4 where 0 is a complete lack of cutaneous involvement and 4 is the severest possible involvement; scores are made independently for each of the areas, h, t, u and l and represents a composite score for each area. An illustration of judging erythema follows: 0 = no erythema, 1 = slight erythema, 2 = moderate erythema, 3 = marked erythema, and 4 = very marked erythema.

The PASI score is calculated according to the following formula:

$$\text{PASI} = 0.1(\text{Eh}+\text{Ih}+\text{Dh})\text{Ah} + 0.3(\text{Et}+\text{It}+\text{Dt})\text{At} + 0.2(\text{Eu}+\text{Iu}+\text{Du})\text{Au} + 0.4(\text{El}+\text{Il}+\text{Dl})\text{Al}$$

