2.2 Benefits and Risks to Subjects

Despite the availability of various PsA therapies, many subjects still do not respond adequately to these treatments, or gradually lose response over time. Risankizumab is an antagonist specific for IL-23 which has been implicated in the pathophysiology of immune-mediated inflammatory diseases. Nonclinical studies have shown that risankizumab has minimal inhibitory effects on IL-12, the inhibition of which has been associated with increased risk of serious infections.^{38,39} Selective IL-23 inhibition may not increase risk of serious infection, including mycobacterial infections.⁴⁰

Interleukin-23 inhibition is not known to increase the risk of tuberculosis (TB) infection or impair the response to TB infection in animal models.^{41,42} Thus, low-risk subjects with positive QuantiFERON testing do not need to be treated with anti-TB therapy prior to receiving risankizumab, but should be carefully monitored for any sign of TB reactivation. Absence of TB reactivation despite not receiving anti-TB prophylaxis will provide important information in humans as to whether TB testing is required prior to treatment with risankizumab.

Efficacy of risankizumab for the treatment of moderate to severe psoriasis was demonstrated in four Phase 3, randomized, placebo- and/or active-comparator (adalimumab or ustekinumab) controlled

pivotal studies in > 2000 subjects. Risankizumab response rates were consistent across all 4 studies: 72% to 75% of subjects achieved 90% reduction in Psoriasis Area and Severity Index score (PASI 90), and 84% to 88% achieved sPGA clear or almost clear at Week 16. In addition, nearly all subjects (85% to 90%) achieved PASI 75 at Week 16.

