3.3 Secondary Endpoints

Ranked secondary endpoints with multiplicity adjustment:

1. Change from Baseline in Health Assessment Questionnaire-Disability Index (HAQ-DI) at Week 24;
2. Proportion of subjects achieving Psoriasis Area Severity Index (PASI) 90 response at Week 24 (in the subset of subjects with a body surface area (BSA) \geq 3% at Baseline);
3. Proportion of subjects achieving ACR20 at Week 16;
4. Proportion of subjects achieving Minimal Disease Activity (MDA) at Week 24;
5. Change from Baseline in 36-Item Short Form Health Survey (SF-36) Physical Component Summary (PCS) at Week 24;

6. Change from Baseline in Functional Assessment of Chronic Illness Therapy-Fatigue (FACIT Fatigue) Questionnaire at Week 24.

Other secondary endpoints without multiplicity adjustment are:

1. Proportion of subjects achieving ACR50 response at Week 24;
2. Proportion of subjects achieving ACR70 response at Week 24;
3. Proportion of subjects with resolution of enthesitis (LEI = 0) at Week 24 in subjects with enthesitis at Baseline;
4. Proportion of subjects with resolution of dactylitis (LDI = 0) at Week 24 in subjects with dactylitis at Baseline;

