3.4 Additional Endpoints

Additional endpoints at the scheduled time points as indicated in [Appendix D](#):

- Proportion of subjects achieving ACR20, ACR50, or ACR70 response;
- Change from Baseline in individual components of ACR response;
- Change from Baseline in LDI in subjects with dactylitis at Baseline;
- Change from Baseline in dactylitis count in subjects with dactylitis at Baseline;
- Proportion of subjects with resolution of dactylitis sites included in the LDI in subjects with dactylitis at Baseline;
- Change from Baseline in LEI in subjects with enthesitis in the LEI at Baseline
- Proportion of subjects with resolution of enthesitis sites included in the LEI in subjects with enthesitis in the LEI at Baseline;
- Change from Baseline in Spondyloarthritis Research Consortium of Canada (SPARCC) Enthesitis Index in subjects with enthesitis in the SPARCC at Baseline;
- Proportion of subjects with resolution of enthesitis sites included in the SPARCC Enthesitis Index in subjects with enthesitis in the SPARCC at Baseline;
- Change from Baseline in total enthesitis count in subjects with enthesitis in the LEI or SPARCC at Baseline;
- Proportion of subjects with resolution of enthesitis in LEI and SPARCC in subjects with enthesitis in the LEI or SPARCC at Baseline;
- Proportion of subjects achieving PASI 75 response (in the subset of subjects with a BSA \geq 3% at Baseline);
- Proportion of subjects achieving PASI 90 response (in the subset of subjects with a BSA \geq 3% at Baseline);
- Proportion of subjects achieving PASI 100 response (in the subset of subjects with a BSA \geq 3% at Baseline);

- Proportion of subjects with both ACR 50 and PASI 90 response (in the subset of subjects with a BSA \geq 3% at Baseline)
- Change from Baseline in BSA-PsO (in the subset of subjects with a BSA \geq 3% at Baseline);
- Proportion of subjects who achieve a Modified Psoriatic Arthritis Response Criteria (PsARC) response;
- Change from Baseline in Disease Activity Score 28 using high sensitivity C-Reactive Protein (DAS28-hsCRP);
- Change from Baseline in PsA Disease Activity Score (PASDAS);
- Change from Baseline in Disease Activity In Psoriatic Arthritis (DAPSA) score;
- Change from Baseline in FACIT-Fatigue Questionnaire;
- Change from Baseline in SF-36 Health Questionnaire;
- Change from Baseline in EuroQoL-5D-5L (EQ-5D-5L) Health Questionnaire;
- Change from Baseline in Work Productivity and Activity Impairment (WPAI) Questionnaire;

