12.0 Overall Type-I Error Control

A multiple testing procedure will be used to provide strong control of the type 1 error rate at $\alpha = 0.05$ (2-sided) across analyses comparing risankizumab versus placebo with respect to the primary and the ranked secondary endpoints for Period 1.² Specifically, the testing will utilize a fixed sequence of hypothesis testing for the primary endpoint followed by the ranked secondary endpoints in the order as specified in Section 3.2. The test starts with the primary endpoint using two-sided $\alpha = 0.05$; testing can be conducted for a lower ranked endpoint only if the previous endpoints in the sequence meet the requirement of statistical significance.

The graph for the testing procedure is provided in Figure 3. In the graph, the arrows specify the α transfer paths. Once an endpoint is rejected (i.e., deemed statistically significant) at its assigned significance level, its significance level will be transferred to the subsequent endpoint following the arrow.

Figure 3. Graphical Testing Procedure

ACR 20 = 20% improvement in American College of Rheumatology criteria; CFB = change from baseline; DMARD-IR = disease-modifying antirheumatic drugs-intolerant or inadequate responder; FACIT Fatigue = Functional Assessment of Chronic Illness Therapy-Fatigue; HAQ-DI = Health Assessment Questionnaire-Disability Index; MDA = minimal disease activity; PASI 90 = 90% improvement in Psoriasis Area and Severity Index in subjects with BSA \geq 3% at baseline; SF-36 PCS = Short Form-36 Physical Component Summary

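### Operations Manual Appendix G sets PASI response at more than an X% reduction, a threshold that no observed score can meet for PASI 100

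*Protocol*

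**What the plan says.** Appendix G of the Operations Manual (itself Appendix F of the protocol) describes the PASI as a score for "overall psoriasis disease state, ranging from 0 to 72". The three severity signs "are assessed using a numeric scale 0 – 4 where 0 is a complete lack of cutaneous involvement", and they are combined with regional area scores of 0 to 6. One sentence then deals with responder endpoints. It opens "The endpoints used are based on the percent reduction from baseline, generally summarized as a dichotomous outcome" and ends by calling this a "dichotomous outcome based on achieving over an X% reduction (or PASIX), where X is 50, 75, 90, and 100".

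No other section gives an operator:

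- Protocol 3.3 ranks "Proportion of subjects achieving Psoriasis Area Severity Index (PASI) 90 response at Week 24" second among the multiplicity-adjusted secondary endpoints and states no cut-off rule. SAP 3.2 does the same.
- Protocol 3.4 lists "Proportion of subjects achieving PASI 100 response" beside PASI 75 and PASI 90, and SAP 3.3 lists all three. Neither gives a rule.
- The SAP's legend to Figure 3 (section 12.0) has "PASI 90 = 90% improvement in Psoriasis Area and Severity Index". Protocol 2.2, on earlier psoriasis studies, has "90% reduction in Psoriasis Area and Severity Index score (PASI 90". Neither says more than, and neither says at least.
- SAP 8.2 and SAP Appendix E derive endpoints of this type by dichotomizing the continuous score after imputation, without naming the inequality.

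By contrast, Operations Manual Appendix E writes every ACR threshold inclusively.

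**The concern.** A strict inequality at X = 100 cannot be satisfied on a scale whose floor is zero. A programmer who looks for a written PASI responder rule finds only this one, and at one of its four stated values it cannot work. At 75 and 90 it can work, but it moves subjects who land exactly on the threshold into the non-responder group. PASI 90 at Week 24 is in the tested sequence, and the combined PASI 90 and ACR50 endpoint in protocol 3.4 and SAP 3.3 takes over the same rule. What is at stake is a single, usable definition for these endpoints, including one that supports a controlled claim.

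**Working it through.** **Inputs.** The PASI formula, area scores 0–6 and sign scores 0–4 come from Operations Manual Appendix G. The Phase 2 Week 16 rates come from protocol 4.2: PASI 75/90/100 of 70%/67%/50% on the regimen of Weeks 0, 4 and 16, and 10%/10%/10% on placebo. Score distributions and the size of the PASI subset are not in the documents and are assumed below.

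**1. Score range.** Maximum = (0.1 + 0.3 + 0.2 + 0.4) × (4 + 4 + 4) × 6 = 1.0 × 12 × 6 = 72. Minimum = 0. This reproduces the stated range.

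**2. Largest possible reduction.** Percent reduction = 100 × (baseline − follow-up) / baseline. With follow-up = 0 this is exactly 100 for any baseline above 0. Exceeding 100 would need a negative score.

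**3. Which baselines are affected.** All attainable totals were enumerated in exact tenths, with area and severity in a region both zero or both nonzero. There are 697 values, 696 of them nonzero.

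| Endpoint | Nonzero baselines from which the exact threshold can be reached |
|---|---|
| PASI 75 | 176 of 696 (25.3%) |
| PASI 90 | 70 of 696 (10.1%), at whole-number baselines such as 12.0 falling to 1.2 |
| PASI 100 | 696 of 696 |

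At X = 100, the inclusive rule makes full clearance a response from all 696 baselines, and the strict rule from none.

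**4. How many subjects that is for PASI 90.** The share of attainable baselines is not the share of subjects. In an illustrative simulation of mild-to-moderate scores, with PASI 90 rates ranging from about 14% to 88%, exact 90% reducers made up 0.3% to 0.6% of subjects. In a separate component-level simulation (assumed median baseline about 6.5 to 7.4, PASI 100 about 50%), replacing the inclusive rule by the strict one moved PASI 90 from 67.6% to 67.2% and PASI 75 from 88.5% to 88.0%. A second scenario with larger baseline area gave 70.2% to 69.8% and 90.3% to 89.9%.

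**5. Effect on the ranked test.** Assume 80 subjects per arm with the required skin involvement, the Phase 2 rates, and a deliberately exaggerated 5-point fall in the active arm (67% to 62%). The difference is 0.62 − 0.10 = 0.52. Its standard error is √[(0.62 × 0.38 + 0.10 × 0.90)/80] = √(0.3256/80) = 0.064, so the difference is about 8 standard errors. Power stays above 0.999 at 80, 100 and 120 per arm.

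**6. Imputed scores.** SAP Appendix E imputes COVID-related missing PASI on the continuous scale and states no bounds. The only truncation rule in the SAP is in Appendix F, for the HAQ-DI tipping point. If an imputed PASI fell below 0, the literal rule could count that subject as a PASI 100 responder while excluding every subject observed to be clear. The text leaves this possible; it is not a prediction.

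**The case against.** The sentence is hedged: endpoints are said to be summarized this way generally. It also lists X = 50, which is not an endpoint in protocol 3.3 or 3.4 or SAP 3.2 or 3.3. It therefore reads as a loose description of the instrument, and protocol 7.1 leaves analysis detail to the SAP. The SAP legend uses the same shorthand for ACR20, which Operations Manual Appendix E defines inclusively, so an inclusive PASI rule is the natural reading. All of this stands as an account of intent. It does not supply a rule: the SAP never states the inequality, and the one that is written fails at X = 100.

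A reader might go further and infer that PASI 100 will be reported as 0% in both arms, wiping out a difference like the 40 points (50% − 10%) seen in Phase 2. The documents do not support that as an expected consequence. They list PASI 100 as an endpoint and report nonzero Phase 2 rates, so full clearance was plainly counted. Those rates are also Week 16 results from the skin-involved subset of a 42-subject arm, not forecasts for Week 24 here.

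A reader might also infer that ranked PASI 90 is compromised, or that the SAP flatly contradicts Appendix G on it. The conflict at 90 rests only on a plain reading of a figure legend and a background paragraph, neither of which says at least, and step 5 shows that the test is not at risk.

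**Conclusion.** The concern holds as a minor point: the rule is wrong as written. The contradiction at PASI 100 is direct and needs no assumption beyond the score's floor of 0. At PASI 75 and PASI 90 the wording misclassifies only exact-threshold subjects. The PASI 90 shift is under 1 point, which rests on assumed score distributions. The statement that its test is safe rests on Phase 2 response rates and an assumed 80 to 120 subjects per arm in the subset. PASI 100 is outside the fixed testing sequence in SAP 12.0 and carries nominal p-values only (SAP 8.5), so no controlled conclusion depends on it. Which inequality will actually be programmed cannot be determined from the documents.

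**What to change.** - In Operations Manual Appendix G, change the threshold from more than X% to at least an X% reduction from baseline.
- In SAP 3.2/3.3, state once that PASI 75, 90 and 100 response means a percent reduction from baseline ≥ 75, ≥ 90 and ≥ 100, applied identically to observed and imputed scores.
- In SAP Appendix E, truncate imputed PASI values to 0–72. Without this, a negative imputed value would meet the ≥ 100% rule without being a score of 0. With it, PASI 100 and a score of 0 are the same thing.

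The cost is one sentence in the manual and two in the SAP, best settled before the Week 24 database lock and unblinding. Nothing changes in data collection, sample size or patient management.
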